5.7.3. Permitted Concomitant Medications

Permitted medications would include:

- Phosphate supplements:

Nirogacestat has been associated with hypophosphatemia, which may require phosphate supplementation. The choice of phosphate replacement, as well as the duration, is at the investigator's discretion.

- Palliative care:

Medications for the standard management of symptoms or supportive care for the management of the effects of study treatment may be administered at the investigator's discretion, unless they are excluded concomitant medications (Section 5.7.2.).

5.7.4. Treatment of Overdose

Overdose

For this study, any dose of study treatment greater than 450 mg daily dose of study treatment within a 24-hour period will be considered an overdose.

In the case of accidental overdosing with nirogacestat:

- Contact the Protocol Director / IND-holder, [name], immediately at: [contact] and/or [contact].
- In the event of an overdosage, stop treatment with nirogacestat and initiate general supportive measures. Due to the high level of protein binding, nirogacestat is not expected to be dialyzable in patients with normal serum protein levels.
- Vital functions should be monitored carefully in an appropriate health care facility. Special attention should be given to hematological (complete blood counts with differential) and gastrointestinal functions.
- Closely monitor the subject for any AE/SAE and laboratory abnormalities for at least 4 days.

Decisions regarding dose interruptions or modifications will be made by the investigator based on the clinical evaluation of the participant.

6. STUDY PROCEDURES AND ASSESSMENTS

6.1. Schedule of Events

Cycle Length: 28 days

Labs, Tests, Procedures, Drug Administration ^a	Screening ^b	Cycles 1–6 ^c	Cycles 7 – 26 ^c	End of Treatment (EOT) ^d
Nirogacestat ^e		X	X	
Cryoablation ^f		X		
Informed consent	X			
Demographics	X			
Medical history	X			
Concomitant medications ^g	X	X	X	X
Physical exam	X	X	X	X
Vital signs	X	X	X	X
Height	X			
Weight	X	X	X	X
Performance status	X	X	X	X
EQ-5D-3L questionnaire ^h	X	X	X	X
CBC w/differential ⁱ	X	X	X	X
Serum chemistry, magnesium, phosphorus ^j	X	X	X	X
Coagulation (PT, PTT)	X			
β-HCG ^k	X			
Urine pregnancy test ^l		X	X	X
ECG ^m	X			
Adverse event evaluation ⁿ	X	X	X	X
Tumor measurements ^o	X	X	Tumor measurements at Screening, then every 3 cycles (every 12 weeks ± 14 days) until End of Treatment (EOT) Visit. Subjects who come off treatment for reasons other than progressive disease may have imaging for EOT visit at the discretion of the provider.	
Radiologic evaluation (MRI) ^o	X	X	Radiologic evaluation at Screening, then every 3 cycles (every 12 weeks ± 14 days) until EOT Visit. Subjects who come off treatment for reasons other than progressive disease may have imaging for EOT visit at the discretion of provider. Documentation (radiologic or clinical) must be provided for subjects removed from study for PD.	
Archival histology report ^o	X			

Correlative studies ^p	X	X		

a. Unless otherwise specified, visits/procedures must occur within \pm 3 days of the planned visit date.
 
b. Screening procedures must occur within 28 days prior to start of treatment.
 
c. Treatment: Nirogacestat: 150 mg by mouth twice daily for up to 26 cycles. Subjects will be seen on Day 1 of every cycle (Cycles 1 through 6) and then every 3 cycles thereafter (Cycles 9 through 26). Subjects will have physical exam, vital signs, weight, performance status evaluation, side effect review, concomitant medication review at the time of their visit. Nirogacestat will be dispensed to subjects during scheduled study visits. See also footnote a.
 
d. Treatment: Cryoablation: Cryoablation procedure (single session, 1 tumor mass) may occur anywhere between Cycles 3 and 4; however, imaging (staging scan) should be done prior to cryoablation procedure.
 
e. Concomitant medications will be recorded from the time the subject signs informed consent and for 30 days after last treatment.
 
f. EQ-5D-3L questionnaire will be completed by subjects at screening, at Cycles 1 thru 3 and Cycles 5 through 9, then every 3 cycles (Cycles 12 through 26) before any assessments are performed, and at EOT. There will not be a questionnaire for Cycle 4. Questionnaires are attached in Appendices I (English), J (Spanish), K (Simplified Chinese), and L (Vietnamese).
 
 Non-in-person visits: For those cycles where participants are not coming to clinic either due to protocol (ie, Cycles 7 & 8) or due to Covid-19 restrictions, participants will be sent the EQ-5D-3L questionnaire via secure Stanford Email or MyHealth Epic message to complete and return via secure Email or MyHealth Epic message. 
g. CBC with differential 
 Should be done within 72 hours prior to Day 1 of each cycle (for Cycles 1 through 6) CBC with differential should be every 3 cycles thereafter (Cycles 9, 12, 15, 18, 21, 24) within 7 days prior to Day 1 of the cycle. CBC with differential should be done within 7 days prior to End of Treatment visit. 
 
h. Serum Chemistry (Metabolic comprehensive panel plus magnesium and phosphorus) includes: albumin, alkaline phosphatase, AST, ALT, bicarbonate, BUN, calcium, chloride, CO₂, creatinine, glucose, globulin, potassium, sodium, total bilirubin, total protein, plus magnesium and phosphorus. 
 Laboratory assessments should be done within 72 hours prior to Day 1 of each cycle (for Cycles 1 through 6). Laboratory assessments should be done every 3 cycles thereafter (Cycles 9, 12, 15, 18, 21, 24) within 7 days prior to Day 1 of each cycle. Laboratory assessments should be done within 7 days prior to End of Treatment visit. 
 
i. B-HCG: A serum pregnancy test (women of childbearing potential) will be performed at screening within 28 days prior to start of treatment. This test can be omitted if subject is post-menopausal by history.
 
j. Urine pregnancy test for women of childbearing potential (this test can be omitted if subject is post-menopausal by history) 
 A urine pregnancy test (should be performed within 72 hours prior to Day 1 of each cycle (for Cycles 1 through 6) Urine pregnancy test should be done every 3 cycles thereafter (Cycles 9, 12, 15, 18, 21, 24) within 7 days prior to Day 1 of the cycle. A urine pregnancy test (women of childbearing potential) should be done within 7 days prior to End of Treatment Visit. 
 
k. Electrocardiogram (ECG): To be done at Screening. Further ECGs are to be performed if indicated.
 
l. Adverse events (AEs) recorded from the time the subject signs informed consent and for 30 days from the time of last treatment. If removed from study due to unacceptable adverse event(s) toxicity, the subject will be followed & safety data collected for at least 30 days or until resolution or stabilization of the adverse event, to the extent possible. SAEs will be followed for 30 days after the last dose of study treatment, or until the SAE(s) is/are resolved or stable whichever is longer. Females reporting dysfunction including ovarian failure, menopause, premature menopause, and/or amenorrhea, will be tracked until resolution or for at least 90 days after discontinuing study treatment. Pregnancies will be followed until outcome is known. See also Sections 3.8, 5.6, 7.2.4, and 7.6.
 
m. Radiologic evaluation and tumor measurements should be performed at Screening, then every 3 cycles (ie, every 12 weeks \pm 14 days) and End of Treatment visit. Subjects who come off treatment for reasons other than progressive disease may have imaging for EOT visit at the discretion of the provider. MRI scan will be used at screening and at subsequent time points). Imaging must encompass all areas of disease.
 
n. Archival histology report will be reviewed for verification of diagnosis. Subjects must have a diagnosis of desmoid tumor/desmoid fibromatosis on pathology report.
 
o. EOT: EOT visit to be done within 30 days of last treatment \pm 7 days. Subjects may be seen in person, by video visit, or may be contacted by phone. Routine labs, AE assessment, conmed review, performance status assessment, and imaging will be done. If subject has in-person visit, physical exam will be performed, and vital signs, weight, and performance status will be evaluated. Other assessments to be done at discretion of the treating investigator. If a video visit or phone visit is done, then EQ-5D-3L questionnaire will be sent to the subject via secure Email or MyHealth Epic message for the subject to complete and return via secure Email or MyHealth Epic message.
				

p. Correlative studies (Optional archival tumor sample and biopsies). If subjects elect to opt-in to correlative studies, archival tumor sample will be requested at screening, and biopsies will be obtained at the time of cryoablation.

6.2. Description of Procedures and Assessments

6.2.1. Efficacy Assessments

Screening tests, examinations, or procedures to be done as part of the study to support the determination of efficacy include:

- Radiologic evaluation and tumor measurements: Imaging must encompass all areas of disease. MRI scan will be used at screening and at subsequent time points.

Assessments (after screening) to support the determination of efficacy include:

- Radiologic evaluation and tumor measurements should be performed at Screening, then every 3 cycles (ie, every 12 weeks \pm 14 days), and End of Treatment Visit. MRI scan will be used at screening and at subsequent time points. Imaging must encompass all areas of disease.

6.2.2. Safety and Other Assessments

Screening assessments, including coagulation tests (PT, PTT) and a serum pregnancy test for women of childbearing potential, must occur within 28 days prior to start of treatment. All other laboratory assessments must be done within 72 hours of C1D1. Serum pregnancy test can be omitted if subject is post-menopausal by history.

Women of childbearing potential must agree to use highly effective contraception for the duration of study participation and for at least 1 week after the final dose of study medication. Sexually active males must agree to use highly effective contraception for the duration of study participation and for at least 1 week after the final dose of study medication (see also Appendix H). Women should not donate or harvest their eggs (ova, oocytes) while participating in this research study and for at least 6 months after taking their last dose of study drug. Men should not donate or preserve their sperm for at least 90 days after taking their last dose of study drug.

Screening tests, examinations, or procedures include:

- **Demographics:** Date of birth, sex, race, ethnicity
- **Medical history review:** Review of medical history, including cancer history and other cancer treatments subject has received.
- **Medication review:** Review of any medications subject is taking now or has recently taken, including any over-the-counter medications.
- **Physical exam and vital signs:** A complete physical exam including vital signs (temperature, heart rate, respiratory rate, blood pressure, height, and weight). Height will only be obtained at screening visit.
- **ECOG Performance Status:** Subject will be asked about their ability to perform everyday tasks (see Appendix B. ECOG Performance Status).

- **Blood samples:** Routine laboratory assessments
 - CBC with differential, platelets
 - Serum chemistry: Comprehensive metabolic panel, plus magnesium and phosphorus
 - Coagulation: PT and PTT
- **Research samples:**
 - **Blood sample for research: Pregnancy test: β -HCG**
 - **Tissue sample for research:**
 - **Archival tumor sample** will be requested by pathology, if subjects elect to opt-in to optional tissue collection for correlative studies.
- **EQ-5D-3L Questionnaire:** Subjects' quality of life will be assessed.

The EQ-5D-3L questionnaire (Appendix I to L) includes questions for following five dimensions: mobility, self-care, usual activities, pain/discomfort and anxiety/depression. Each dimension has 3 levels: no problems, some problems, and extreme problems. The subject is asked to indicate his/her health state by ticking the box next to the most appropriate statement in each of the five dimensions.

- **Electrocardiogram (ECG):** At screening ECG, QT interval corrected by Fridericia's formula must not be > 450 msec for male subjects or > 470 msec for female participants, or > 480 msec for participants with bundle branch block after electrolytes have been corrected (Exclusion criteria 9). Further ECGs to be done at discretion of treating investigator.
- **Radiologic evaluation and tumor measurements:** Imaging must encompass all areas of disease.
- **Archival histology report:** Pathology reports will be reviewed for verification of diagnosis. Subjects must have a diagnosis of desmoid tumor on pathology report. Central review, for verification of diagnosis, will not be done.

Enrollment: Subjects must have progressive or symptomatic desmoid tumor.

Subjects will all be assigned to receive the same treatment: systemic therapy with nirogacestat for 3 cycles, followed by 1 session of cryoablation between Cycles 3 and 4, followed by nirogacestat for Cycles 4 through 26.

The duration of enrollment for this study will last approximately 24 months.

Assessments (after screening):

- Unless otherwise specified, visits/procedures must occur within ± 3 days of the planned visit date.
- **Subjects will be seen Day 1 each cycle (C1 through C6) and then Day 1 of every 3 cycles (= approximately every 12 weeks ± 7 days, ie, C9, C12, C15, C18, C21, C24) and have the following assessments.** If an in-person visit is not allowed secondary to Covid-19, then a video visit or contact by phone is allowed.

- Physical exam, vital signs, weight
- EQ-5D-3L Questionnaire: Subjects' quality of life will be assessed at multiple timepoints throughout the study. The EQ-5D-3L questionnaire will be completed at Cycles 1 through 3 and Cycles 5 through 9, then every 3 cycles thereafter (Cycles 12, 15, 18, 21, 24), and at the EOT visit. There will not be a questionnaire for Cycle 4.
 - The questionnaire will be completed at specified study visits before any assessments are performed.
 - Non-in-person visits: For those times where subjects are not coming to clinic for an in-person visit, either due to protocol (ie, Cycles 7 and 8) or due to Covid-19 restrictions, an EQ-5D-3L questionnaire will be emailed to the subjects via secure Stanford Email or MyHealth Epic message for subject completion and return via secure Email or MyHealth Epic message.
 - The EQ-5D-3L questionnaire will then be completed every 3 cycles thereafter (Cycle 12, Cycle 15, etc.), and at the EOT visit). The questionnaire will be completed at each study visit before any assessments are performed.
- Side effect review, concomitant medications review, performance status assessment
- **Laboratory assessments:**
 - **Blood samples will be drawn for routine tests** every cycle within 72 hours prior to Day 1 of Cycles 1 through 6. Blood samples will be drawn for routine tests every 3 cycles thereafter (approximately every 12 weeks) within 7 days prior to D1 of cycle (Cycles 9, 12, 15, 18, 21, 24) and at the End of Treatment visit.
 - **Research-related Laboratory Assessments: Urine pregnancy test** will be done every cycle within 72 hours prior to Day 1 of Cycles 1 through 6. Urine pregnancy test will be done every 3 cycles thereafter (approximately every 12 weeks) within 7 days prior to D1 of cycle (Cycles 9, 12, 15, 18, 21, 24) and at the End of Treatment visit.
- **Tissue samples for research: Optional**
 - **Biopsies** will be obtained at the time of cryoablation (between Cycle 3 and 4) for correlative studies if subjects elect to opt-in to optional tissue collection for correlative studies. Biopsies may be saved for future research.
- **Radiologic evaluation and tumor measurements** should be performed at screening, then every 3 cycles (ie, every 12 weeks \pm 14 days), and End of Treatment. MRI scan will be used at screening and at subsequent time points. Imaging must encompass all areas of disease.
- **Adverse events:** Adverse events will be assessed from the time the subject signs consent until 30 days after last treatment. If a subject is removed from study due to unacceptable adverse event(s) toxicity, that subject will be followed and safety data collected for at least 30 days and until resolution or stabilization of the adverse event, to the extent possible.

End of Treatment:

An End of Treatment visit will be done within 30 days of last treatment \pm 7 days. Subjects will be followed for safety for 30 days from time of last treatment, except if being monitored for related adverse event.

The following procedures/assessments may be performed at the EOT visit:

- Subjects may be seen in person, by video visit, or may be contacted by phone. If in-person visit, then physical exam, vital signs, weight and EQ-5D-3L questionnaire will be done.
- If a video visit or phone visit is done, then EQ-5D-3L questionnaire will be sent to the subject via secure Email or MyHealth Epic message for the subject to complete and return via secure Email or MyHealth Epic message.
- Vital signs and weight will be done if subject has in-person visit.
- EQ-5D-3L Questionnaire: See above.
- Adverse event assessment
- Review of concomitant medications
- Performance status assessment
- Routine labs
- Urine pregnancy test
- Radiographic evaluation and tumor measurement: Subjects who come off treatment for reasons other than progressive disease may have imaging for EOT visit at the discretion of the provider.
- Other assessments to be done at the discretion of the treating investigator.

Subjects that personally withdraw from treatment will be requested to have a 30-day End of Treatment visit or otherwise receive a follow-up contact, unless specifically countermanded by the subject.

7. ADVERSE EVENTS AND REPORTING PROCEDURES

References for SCI adverse event (AE) policies and practices are provided in Appendix A.

7.1. Adverse Event Definitions

An adverse event is any untoward medical occurrence associated with the use of a drug in humans, whether or not considered drug-related. An adverse event can be any unfavorable and unintended sign or symptom, including abnormal laboratory findings, or disease, that is temporally associated with the use of a drug, and does not imply any judgment about causality. An adverse reaction is any event that is caused by a drug or device, ie, possibly-, probably-, or definitely-related to the use of the drug or device.

Except as otherwise explicitly defined within this section, **this also includes all events of clinical deterioration such as tumor relapse, recurrence, or upstaging, or new cancers.**

Within the scope of this study and protocol, adverse device effects, ie, events that have a serious adverse effect on health or safety or any life-threatening problem or death caused by, or associated with, a device may be referred to as "serious adverse events (SAEs)."

Serious adverse events (SAEs) are defined per the FDA definition at [21CFR§312.32\(a\)](#) and [ICH GCP E6](#). An adverse event is considered "serious" if, in the opinion of the PD, investigator, or sponsor, it results in ANY of the following.

- Death
- Life-threatening adverse event with an **actual and immediate risk of death** [21CFR§312.32(a)]
- In-patient hospitalization or prolongation of existing hospitalization, except planned hospitalization or hospitalization only for study conduct will not be considered SAEs. Note that the per-protocol cryoablation procedure will not be considered an SAE hospitalization, even if the patient stays in the clinic overnight.
- A persistent or significant incapacity or substantial disruption of the ability to conduct normal life functions
- A congenital anomaly/birth defect
- Event jeopardizes the subject and may require medical or surgical intervention to prevent one of the outcomes listed here

7.2. **Classification of Adverse Events**

7.2.1. **Severity of Event**

NCI CTCAE version 5.0 is used to assess the severity of adverse events in this study.

7.2.2. **Adverse Event Attribution to Intervention or Study**

For this study, all recorded adverse events will be assessed on the basis of whether or not the adverse event was caused by / due to (ie, related) to the study intervention(s). AEs, serious or otherwise, will be attributed by the Principal Investigator or qualified designate to study treatment in accordance with the definitions below.

 Definitely Related. There is clear evidence to suggest a causal relationship, and other possible contributing factors can be ruled out. The clinical event, including an abnormal laboratory test result, occurs in a plausible time relationship to study intervention administration and cannot be explained by concurrent disease or other drugs or chemicals. The response to withdrawal of the study intervention (dechallenge) should be clinically plausible. The event must be pharmacologically or phenomenologically definitive, with use of a satisfactory rechallenge procedure if necessary. Probably Related. There is evidence to suggest a causal relationship, and the influence of other factors is unlikely. The clinical event, including an abnormal laboratory test result, occurs within a reasonable time after administration of the study intervention, is unlikely to be attributed to concurrent disease or other drugs or chemicals, and follows a clinically reasonable response on withdrawal (dechallenge). Rechallenge information is not required to fulfill this definition. Potentially / Possibly Related. There is some evidence to suggest a causal relationship (eg, the event occurred within a reasonable time after administration of the trial medication). However, other factors may have contributed to the event (eg, the participant's clinical condition, other concomitant events). Although an adverse event may rate only as "possibly related" soon after discovery, it can be flagged as requiring more information and later be upgraded to "probably related" or "definitely related," as appropriate. 	These are treated as " Related "

 Unlikely to be related. A clinical event, including an abnormal laboratory test result, whose temporal relationship to study intervention administration makes a causal relationship improbable (eg, the event did not occur within a reasonable time after administration of the study intervention) and in which other drugs or chemicals or underlying disease provides plausible explanations (eg, the participant's clinical condition, other concomitant treatments). Not Related. The adverse event is completely independent of study intervention administration, and/or evidence exists that the event is definitely related to another etiology. There must be an alternative, definitive etiology documented by the clinician. 	These are treated as " Not Related "

In addition, for adverse events determined "Not Related" to the study intervention(s), the Principal Investigator or qualified designate will attribute the event to the study or procedures according to the definitions above. Note that adverse events can be determined related to both the intervention(s) and/or the study / procedures.

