2.2.2. Secondary Objectives

- To assess the effects of combination therapy with cryoablation plus nirogacestat on efficacy by evaluation of the clinical benefit rate (CBR) at 1 year in subjects with progressive or

symptomatic desmoid tumor. Response will be assessed according to modified RECIST criteria (mRECIST).

- To assess the effects of combination therapy with cryoablation plus nirogacestat on efficacy, by evaluation of median disease progression.
- To assess the effects of cryoablation plus nirogacestat on tumor response (as defined by objective response rate) at 1 year.
- To assess the time to response from the start of treatment with nirogacestat to the first objective tumor response.
- To assess the duration of response from time of response to time of progression.
- To assess safety and tolerability of cryoablation plus nirogacestat in subjects with progressive or symptomatic desmoid tumors.

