7.3. Potential Adverse Events and Risks

A brief summary of nirogacestat adverse events and risks was described in Section 1.3.1 Known Potential Risks.

In addition to the summary risks described in Section 1.3.1, adverse events described by severity and frequency within the research agent nirogacestat Investigator's Brochure and/or the Ogsiveo™ (nirogacestat) package insert are considered anticipated, ie, not unexpected. Procedural risks described in Section 1.3.1 are considered anticipated.

Cryoablation is widely used within the Stanford Cancer Institute for the treatment of cancer, both as an individual treatment as well as part of a treatment regimen, and its risk profile is well understood as a regular medical care procedure. Risks associated with cryoablation are expected in accordance with the current FDA 510k approval. It is not known if there are additional risks of cryoablation in combination with the study drug, nirogacestat. However, safety is being monitored, as described within this section and within Section 6.2.2 (Safety and Other Assessments). Doses of nirogacestat may be adjusted in response to specific adverse events, as described in Section 5.6 (Dose Modifications).

7.3.1. **Nirogacestat** (Information from Investigator's Brochure)⁴ Please also reference the Ogsiveo™ (nirogacestat) package insert.²⁸

Special Warnings and Precautions for Use

To date, important identified risks related to nirogacestat include diarrhea, dermatologic reactions (maculopapular rash, hidradenitis, and folliculitis), ovarian dysfunction, electrolyte abnormalities (hypophosphatemia and hypokalaemia), and elevated liver transaminases. Important potential risks include non-melanoma skin cancer (basal cell carcinoma and squamous cell carcinoma), embryo-fetal toxicity, effects on male fertility, and in pediatric patients, epiphyseal disorder.

- **Diarrhea**

Nonclinical data suggest that inhibition of GS may interfere with the integrity of the lower gastrointestinal tract epithelium and control of intestinal motility. GS inhibition may affect the intestinal tract epithelium (Barker, 2007; Kurokawa, 2020), villus lacteals (Norden, 2021), and enteric nervous system (Willem, 2016; Barrenschee, 2015), and lead to diarrhea.

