7.4.1. Case Report Forms for Adverse Event Reporting

Both SAEs and non-serious adverse events will be described in source documentation and listed on study-specific Case Report Forms (CRFs or eCRFs).

Adverse events will be recorded in an EPIC smartphrase contained within an EPIC clinic note. This will be transcribed into Oncore database. The information will include the unique subject identifier, event preferred term, CTCAE body system, date of occurrence, date of resolution; and type of resolution. All signs, symptoms, significant laboratory findings, AND diagnoses should be recorded, regardless of relationship, except as described in this document. A single “overarching” diagnosis should not be solely entered as the adverse event term in lieu of the full list of observed signs, symptoms, and significant laboratory findings, which may include the diagnostic preferred term.

Types of resolution are:

- “Resolved,” ie, to Grade 0 (or baseline if a pre-existing condition)
- “Continuing” and stable (includes downgrades from a higher grade to a lower grade)
- “Deceased” (due to any cause while on-study)
- Lost-to-follow-up.
- **NOTE:** “Hospitalized” is not an outcome.

Any pre-existing condition that worsens in severity/grade or frequency should be recorded as a new adverse event, except as described in this document.

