Duration of response will be summarized descriptively. If sufficient data are available the distribution will be estimated using the Kaplan-Meier method, and the Kaplan-Meier curves, medians and 95% confidence intervals of the medians will be presented.

Nominal duration of study involvement is 26 months, with last assessment after about 24 months of treatment.

10.2.2.6. **Adverse events and safety**

Adverse events will be tabulated with frequencies and percentages for grade, severity, status and relationship to study drug or study procedure. The analysis population will include all subjects who have started study treatment. Assessment for safety signals will be from time of consent until 30 days after the last treatment.

10.2.3. **Exploratory Endpoints and Analysis**

10.2.3.1. **Patient-reported outcomes (EQ-5D-3L)**

Summary measures (mean, standard deviation, median, interquartile range) of the EQ-5D-3L survey scores will be calculated for each time point during the duration of the study; scores will graphically depicted at each time point. In addition, we will calculate the difference of the scores at the baseline, time of demonstrated clinical benefit rate, and last follow-up date and report summary statistics. Nominal duration of study involvement is 26 months, with last assessment after about 24 months of treatment.

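### Section 7.2.2 does not require a separate nirogacestat and cryoablation relatedness judgement for every adverse event, although Section 10.2.2.6 and Outcome 7 need one

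*Protocol*

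**What the plan says.** Section 7.2.2 of the protocol has all recorded adverse events judged for relatedness to the study intervention(s), on a five-level scale collapsed to Related or Not Related. A second step follows, covering the study or its procedures and limited to one branch: "In addition, for adverse events determined 'Not Related' to the study intervention(s), the Principal Investigator or qualified designate will attribute the event". The next sentence adds: "Note that adverse events can be determined related to both the intervention(s) and/or the study / procedures".

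Cryoablation appears under both labels. Section 4 is headed as the study intervention, and within it Section 4.2 places cryoablation among other procedures. The synopsis names the drug and the procedure as separate things, while Section 7.4 applies the word interventional to drug, device and procedure alike. Section 7.2.2 does not settle which label it uses.

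Two outputs depend on this rule. Section 10.2.2.6, like the synopsis, tabulates events by grade, severity, status and relationship to study drug or study procedure, in everyone who started study treatment. Outcome 7 in Section 2.3.2.2 reports the number of Grade 3 or higher events that the investigator considers possibly, probably or definitely related to nirogacestat.

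**The concern.** Both outputs assume that each event carries an answer about the drug, and the table also assumes one about the procedure. Section 7.2.2 guarantees neither pair of answers. It asks about the two components jointly, or it asks about the second only when the first has been cleared.

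This matters more here than in a single-agent study because the combination is the investigational element. Section 7.3 says: "It is not known if there are additional risks of cryoablation in combination with the study drug, nirogacestat". Events to which both components may have contributed bear directly on that question, and they are the ones the conditional step handles worst. At stake are the accuracy of the relationship columns and of the nirogacestat-related count reported to the registry.

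**Working it through.** The protocol states no figure on this point, so there is nothing to reproduce. The check is to follow Section 7.2.2 as written for each kind of event, under each reading of what cryoablation is.

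| Investigator's view of the cause | Record if cryoablation is an intervention | Record if cryoablation is a procedure |
|---|---|---|
| Nirogacestat only | Related; second step not required | Related; second step not required |
| Cryoablation only | Related; second step not required | Not Related; then attributed to procedure |
| Both | Related; second step not required | Related; second step not required |
| Neither | Not Related; second step taken | Not Related; second step taken |

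Let *a*, *b* and *c* be the numbers of events in the first three rows.

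**What the outputs need.** The drug column of the Section 10.2.2.6 table needs *a* + *c*. The procedure column needs *b* + *c*. Outcome 7 needs *a* + *c*, restricted to Grade 3 or higher.

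**If cryoablation is an intervention.** The first three rows leave the same record, so only the total *a* + *b* + *c* is known. If Outcome 7 is filled from events marked Related, it is too large by (*a* + *b* + *c*) − (*a* + *c*) = *b*, the cryoablation-only events, within Grade 3 or higher. Neither relationship column can be filled from the required answers.

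**If cryoablation is a procedure.** The drug column and Outcome 7 come out as *a* + *c*, as intended. The procedure column holds only *b*, which is too small by (*b* + *c*) − *b* = *c*, the events related to both. Rows one and three leave the same record, so the missing events cannot be identified afterwards.

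**Does the note on dual relatedness repair this?** It says that an event may be related to both; it does not instruct anyone to ask. It also fits poorly with the step before it. An event reaches the second step only after being judged Not Related to the intervention(s), so no event that takes that step can be related to both.

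Neither reading therefore secures both columns. The documents give no values for *a*, *b* or *c*, so the errors can be stated as terms and directions only.

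**The case against.** The best case for the plan is that the procedure reading is the natural one. The synopsis separates drug from procedure, Section 4.2 calls cryoablation a procedure, and the relatedness definitions use drug language such as dechallenge and rechallenge. On that reading the labels in Section 7.2.2 match those in Section 10.2.2.6, and dual attribution is expressly allowed. This stands in part: it makes the overcount in Outcome 7 the less likely failure. It leaves the undercount of procedure-related events in place, because permission to record both is not a requirement.

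Several stronger readings are tempting, and the documents do not support them.

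- *That the planned table pools the two sources.* It does not; Section 10.2.2.6 and the synopsis both split by relationship. The weakness is in what feeds the split.
- *That the safety of the combination cannot be read.* The objective in Section 2.2.2 is "To assess safety and tolerability of cryoablation plus nirogacestat in subjects with progressive or symptomatic desmoid tumors". All-cause events by grade in everyone treated answer that without component attribution.
- *That grade and relatedness are not collected because Section 7.4.1 omits them.* Its sentence, "The information will include the unique subject identifier, event preferred term, CTCAE body system, date of occurrence, date of resolution; and type of resolution", need not be exhaustive. Section 7.2.1 sets the severity scale, Section 7.2.2 requires relatedness for all recorded events, Section 7.7 requires retained documentation of attribution and seriousness, and Section 9.5 puts relatedness in the serious adverse event log.
- *That the drug-alone lead-in is lost, or that starting collection at consent is an error.* Onset dates are recorded and there is a single cryoablation session, so tables by period can still be made. Their design commonly belongs to a statistical analysis plan.
- *That the quoted rates size the problem.* The 22% Grade 3-4 toxicity for cryoablation and the 16% Grade 3 diarrhea for nirogacestat say how often each toxicity occurs. Neither measures misattribution, and diarrhea is not among the cryoablation effects listed in Section 7.3.2.

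**Conclusion.** The point holds as a mismatch between a data-capture rule and the outputs that rely on it. Followed as written, Section 7.2.2 either omits events related to both components from the procedure column, or leaves the component unnamed and allows cryoablation-only events into the nirogacestat-related count of Outcome 7. Which of these occurs depends on a classification that the protocol does not make. The number of events affected cannot be derived from the document.

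The conclusion assumes that investigators record what the section requires and no more. A site that volunteers both judgements for every event would avoid the problem. It also assumes that the case report form follows the section; the form is not shown. A statistical analysis plan, if one exists, can define the table but cannot supply an attribution that was never made. The correction is worth making for that reason, although the main safety objective does not depend on it.

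**What to change.** In Section 7.2.2, replace the conditional second step with two separate relatedness judgements for every recorded adverse event, one to nirogacestat and one to cryoablation, each made whatever the answer to the other. Name the two components, so that the labels intervention and procedure no longer decide what is asked. Carry both answers on the adverse event record described in Section 7.4.1.

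The drug and procedure columns in Section 10.2.2.6 and the count in Outcome 7 can then be produced as stated, with events related to both counted in each column. The cost is one extra attribution field per event. No change to the analysis population, the reporting window or the table layout is needed.

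If events have already been recorded under the present rule, those marked Related with no procedure judgement should be put back to the investigator for the missing answer.
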